### **Summary of Protocol**

Patients with hypoparathyroidism who meet the inclusion criteria will be admitted to the Clinical Center for an initial inpatient dose-adjustment phase lasting 7-10 days. PTH therapy (via pump) or twice daily subcutaneous injections will be compared in a randomized crossover study consisting of two 3-month treatment arms.

Randomization to either twice-daily or pump PTH therapy will take place at the beginning of the first admission. The initial admission will consist of daily urine and blood collections for mineral levels to determine the best dose of PTH. During the pump arm only, toward the end of the initial dose adjustment phase (day7), there will be a 24h test of serial blood collections to further determine if the dose of PTH is adequate. Patients will be discharged and followed on an outpatient basis for 3 months. During this period, weekly serum and urine mineral levels will be measured. After 3 months, patients will be re-admitted to the Clinical Center. At the beginning of this admission, a 24-h serial test will be performed to measure serum and urine minerals, serum vitamin D and urine cyclic AMP levels. The patients will then cross over to the opposite treatment arm and will undergo the identical measures for the second 3-month treatment arm. The third and final admission will last 3-5 days. At the conclusion of the study, patients will be discharged to their local physicians for care of their hypoparathyroidism. Investigational drug preparation and randomization will be carried out by the NIH Clinical Center Pharmaceutical Development Service. At baseline, 3 months, and 6

months, subjects will undergo evaluation in the Rehabilitation Medicine department for evidence of muscle weakness, decreased stamina and fatigue. This is an important part of the study as we hypothesize PTH therapy will provide a substantial improvement.

### **Inclusion and Exclusion Criteria**

*Inclusion criteria:* This study will include patients of both genders (ages 7-70) with biochemically confirmed chronic hypoparathyroidism of at least one year duration. Twenty-four subjects will be enrolled. We will recruit adults with post-surgical hypoparathyroidism and children with congenital forms of hypoparathyroidism including APS-1 or hypocalcemia due to an activating mutation of the calcium receptor.

*Exclusion criteria:* Subjects who meet any of the following criteria are not eligible for the study. Presence of significant hepatic or kidney disease. Pregnancy. Patients who are calcium infusion dependent and/or do not respond to calcitriol therapy to maintain normal levels of serum calcium will be excluded. Seizure disorder requiring antiepileptic medications.

Exclusion criteria for biodex muscle testing in the RMD: Subjects with the following conditions will not participate in the biodex testing portion of the protocol: Any pathology of right knee or elbow consisting of, but not limited to, joint instability, pain, or evidence of an active inflammatory or infectious process. Skin in these areas must be intact; there can be no open or healing wound of the right knee or elbow.

### **Enrollment and Baseline Data Collection**

Potential subjects will be evaluated for study eligibility through the evaluation of their medical history, lab data and performance of a physical examination by a study investigator.

*Informed consent:* Prior to their admission, eligible subjects will be invited to participate in the study, and the study procedures will be initially discussed over the phone. At their first inpatient admission, eligible adult subjects will be given a consent form to read and, after discussion with the investigators, if they agree to participate, the consent form will be signed. The consent will be discussed with each subject at a level they can understand. Written informed consent must be obtained prior to performing any study-specific procedures that are not part of the subject's routine care.

Prior to obtaining protocol consent, screening labs will be obtained on subjects to determine protocol eligibility. The NIH general admission consent form (NIH-1225-1) will serve to obtain the patient's consent to obtaining this laboratory evaluation.

*Patient evaluations:* There will be three inpatient admissions at baseline, 3 and 6 months in the NIH Clinical Center. Patients with hypoparathyroidism who meet the above criteria will be admitted to the Clinical Center for an initial baseline inpatient evaluation, patients will be randomized to initially receive one of two possible replacement PTH1-34 regimens: (a) given subcutaneously twice daily or (b) pump therapy. PTH therapy will be initiated. and dose-adjustment will proceed to optimize doses and to maintain normal levels of serum calcium, phosphorus and magnesium and to reduce urine calcium levels. After discharge, patients will be followed on an outpatient basis in collaboration with a local physician and lab. Crossover to the other treatment arm occurs at the second inpatient admission.

*Rehabilitation Medicine:* Patients will be seen in Rehabilitation Medicine at baseline, 3 months, and 6 months. Fatigue scale questionnaire, a self measure of impact of fatigue on activity and 6-minute walk-run test, a test of cardiovascular fitness and functional capability, in accordance with the guidelines and methods described and established by the American Thoracic Society. A biodex test of muscle endurance will also be performed. These tests will be administered in the Rehabilitation Medicine Department.

*Nutrition:* A dietary consultation will be obtained at each inpatient admission to determine the patient's usual daily calcium intake, and to review standard recommendations for dietary calcium, given the patient's age and body size. Patients will be instructed to maintain approximately the same calcium intake during the inpatient and outpatient phases. Our recommendation for daily intake is 1000-2000 mg of elemental calcium per day. A fixed diet (time and amount of calcium intake) will be provided during the 24-h testing day.

## Monitoring of Subjects

*Baseline (Admission 1):* Admissions will include height, weight, general medical history, urine pregnancy and a physical exam. Additionally, routine hematological evaluation (CBC), hepatic function studies, mineral panel, alkaline phosphatase, thyroid functions, vitamin D, intact PTH. Daily AM fasting blood: acute care and mineral panels, every other day (x 3 collections) blood and urine collections for bone markers: serum osteocalcin, bone specific alkaline phosphatase, 24-hour urine pyridinium crosslinks. Daily 24-hour urine collections will be obtained for measurement of calcium, phosphate, magnesium, and creatinine clearance. Patients will fill out a symptom questionnaire to determine their symptoms related to hyper- or hypocalcaemia. At the 3-month and 6-month time points, the response to therapy will be compared and examined over a 24-h period with every 2 h measures of mineral levels in the serum and every 4 h measures in the urine. Fatigue scale questionnaire (Self measure of impact of fatigue on activity) and 6-minute walk-run test, and a Biodex test for muscle endurance will be administered in the Rehabilitation Medicine Department at baseline, 3, and 6-month time points.

1. The Clinical center admission 1 and 2 will last approximately 10-12 days and include the following:

- Monitoring of effects of PTH with q12 hr serum calcium levels: Twice daily blood calcium levels may be performed during the initial days of pump therapy monitoring to identify the optimal basal rate. The PI will determine the need for serum calcium levels at this frequency.
- If a subject reports symptoms of hypocalcemia, the blood calcium will be checked. When the blood calcium is  $<1.7$  mmol/L mg/dL, the subject will receive treatment for hypocalcemia by increasing the dose, providing calcium carbonate (600 mg calcium PO) or with 1 cup of calcium fortified orange juice. Additional calcium measurements will be made as needed until the blood calcium is  $>1.8$  mmol/L
- Subcutaneous injection or pump teaching
- Assessment of the baseline pre-PTH measures of fatigue endurance and muscle strength and endurance.
- Day 7, pump subjects will have repeated serum mineral testing every 2 hours for 24h to further refine dose adjustment. This test will be done at the beginning of the pump arm and will provide more information to determine the dose. If there are patient care issues that indicate that it would be preferable not to perform this test, such as poor intravenous access, the test will not be done.

2. The outpatient phase will last 3 months and include the following:

- Daily PTH therapy as prescribed by study investigators
- Weekly monitoring of serum mineral levels
- Subjects may be asked to obtain more frequent testing if there is any concern with calcemic control
- Measurement of urine calcium and markers of bone turnover on a monthly basis.
- Phone calls to each subject on the first outpatient day and then approximately every 3 days (twice a week) for the first 3 weeks and then weekly until the subject's 3-month follow up admission.
- Occurrence of side effects or adverse events will be solicited during each phone contact and at the 6-month follow-up visit.

3. Second admission to mirror the first admission and will last 10-12 days.

The second admission will occur 3 months after the first visit at which PTH use was first initiated.

- Subject will arrive in the NIH CC for admission. Monitoring of serum and urine mineral levels for three days.

- On admission day 4 an intravenous catheter will be inserted for repeated serum calcium phosphorus, magnesium, 1, 25 OH vitamin D measurements. Blood measurements will be made every 2 h and urine collections every 4 h.

4. Third admission will be identical to the second admission and will contain the repeated testing on admission day 4.

- The subject will be given a small supply of PTH (2 weeks, at the identical dose to PTH injection therapy as determined during this study), while he/she awaits his/her first outpatient visit with the primary care physician.
- There will be a phone contact approximately 4 days after discharge to review hypoparathyroid management and to make adjustments. Additional contacts will be made, if necessary, with their local physician.
- Rehabilitation Medicine consult. Patients will fill out a symptom questionnaire to determine their symptoms related to hypo- or hypercalcemia. Rehabilitation consult as described above.

*Outpatient blood and urine collections:* Each subject will be discharged with clear instructions on medication doses and follow-up procedures for adjusting their medications. Every week for the first month, and then twice monthly, protocol patients will go to a local laboratory near their home for measurement of serum mineral and alkaline phosphatase values. These data will be used to monitor and adjust the PTH dose.

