### 93     **Objectives**

94     The primary objective of this pilot study will be to evaluate the safety, biological activity and  
95     pharmacodynamics of PTH 1-34 comparing delivery by twice daily subcutaneous injection vs. an insulin pump.  
96     The levels of serum calcium, phosphorus, magnesium, 1,25 OH vitamin D, bone markers, and mineral levels  
97     and cyclic AMP in the urine are the key physiologic responses to determine the adequacy of the PTH effect on  
98     hypoparathyroidism. We hypothesize that the delivery of PTH via pump therapy will maintain serum calcium  
99     in the normal range with minimal or no fluctuations in blood mineral levels. We anticipate that the small  
100     increments of PTH released by the pump will result in a normal physiologic pharmacodynamic profile of

serum calcium, magnesium, phosphorus and 1,25 vitamin D, normalize urine calcium and cause mild increases in urinary phosphorus and cAMP with no apparent peaks or troughs throughout the day.

This protocol is being conducted to study PTH delivered via pump vs. twice daily subcutaneous injections. PTH therapy via pump or twice-daily subcutaneous injections will be compared in a randomized crossover study consisting of two 3-month treatment arms.

The specific hypotheses and study endpoints are as follows:

We hypothesize that PTH pump therapy will be better tolerated, more convenient, and the preferred treatment modality. We expect that pump delivery of PTH will provide smoother metabolic control of serum and urine mineral levels compared to twice-daily injections. Our premise is that pump delivery will produce a more physiologic delivery of PTH by reducing brief episodes of hyper- and hypocalcemia throughout the day, will

permit improved calcemic control in the blood and will be more physiologic to the bone and kidney, with normal bone markers and reduced urine calcium.

The primary objective of this pilot study will be to evaluate the safety, efficacy, and pharmacodynamics of PTH1-34 given as twice-daily subcutaneous injection compared to an insulin pump. The levels of serum calcium, phosphorus, magnesium in the blood and urine are the key physiologic responses to determine the adequacy of the PTH effect on hypoparathyroidism. We hypothesize that the delivery of PTH via pump therapy will maintain serum calcium in the normal range with minimal or no fluctuations in blood mineral levels.

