We expect that occasional or no episodes of hypo or hypercalcemia will occur during both daily (pre-dose lab testing) or 24 h testing periods. Furthermore, there will be no diminishing effects of the pump's ability to maintain normal mineral homeostasis over the 3-month period.

Secondary objectives are:

Secondary objectives include measuring serum 1,25 OH vitamin D and cyclic AMP in the urine.

Biochemical marker of bone health: markers of bone formation and resorption in the blood and urine.

To determine if PTH therapy provides significant relief to patients with hypoparathyroidism who generally complain of debilitating fatigue, muscle weakness and decreased endurance. Fatigue scale questionnaire, a self measure of impact of fatigue (15) on activity and 6-minute walk-run test, a test of cardiovascular fitness and functional capability, in accordance with the guidelines and methods described and established by the American Thoracic Society (16,17). A biodex test of muscle endurance will also be performed. These tests will be administered in the Rehabilitation Medicine Department. These measures may help determine if PTH provides significant improvement of these symptoms. This section of the protocol will be performed by the Rehab Medicine collaborators.

**Study Design/Sample Size:** Study including 24 subjects with chronic hypoparathyroidism comparing PTH pump delivery vs twice daily PTH 1-34 injections.

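### Nothing in the supplied text keeps the Rehabilitation Medicine testers unaware of the regimen, so tester expectation could bias the pump-injection comparison on the walk-run and Biodex tests

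*Combined protocol and SAP*

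**What the plan says.** All references are to the combined protocol and SAP.

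- **Tests and timing.** Monitoring of Subjects places the fatigue questionnaire and the 6-minute walk-run test in Rehabilitation Medicine, and adds that "a Biodex test for muscle endurance will be administered in the Rehabilitation Medicine Department at baseline, 3, and 6-month time points". Summary of Protocol and Enrollment and Baseline Data Collection give the same schedule.
- **Who runs them.** Objectives: "This section of the protocol will be performed by the Rehab Medicine collaborators".
- **Design.** Objectives: "PTH therapy via pump or twice-daily subcutaneous injections will be compared in a randomized crossover study consisting of two 3-month treatment arms". Enrollment and Baseline Data Collection adds: "Crossover to the other treatment arm occurs at the second inpatient admission". The order of the month-3 functional tests and the switch is not given.
- **Stated aim of these tests.** The secondary objective begins "To determine if PTH therapy provides significant relief to patients with hypoparathyroidism". The first admission includes "Assessment of the baseline pre-PTH measures of fatigue endurance and muscle strength and endurance".
- **Stated expectations.** On the regimens, Objectives says: "We hypothesize that PTH pump therapy will be better tolerated, more convenient, and the preferred treatment modality". On the Rehabilitation Medicine evaluation, Summary of Protocol says: "This is an important part of the study as we hypothesize PTH therapy will provide a substantial improvement".
- **Masking.** The supplied text does not mention blinding or masking of subjects, investigators or testers.
- **Standardisation.** The walk-run test is to follow American Thoracic Society methods. That reference is attached to the walk test and not to Biodex.

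**The concern.** Walk distance and muscle endurance are performance measures. The result depends on the subject's effort, and that effort responds to the tester's instructions and encouragement. If testers know who is on the pump, and expect more or less from it, they may coach differently by regimen without meaning to.

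The crossover does not protect against this. Randomised order balances period effects, but a bias that follows the regimen goes with it into whichever period it falls and stays in the within-subject difference. It could produce a false difference or mask a real one.

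Subjects and the staff who set doses must know the regimen. Staff in a separate department who run a walk test and a Biodex test do not need to. At stake is whether a pump-injection finding on these two tests can be interpreted.

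**Working it through.** **Step 1. Which comparisons can these tests support?**

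- *Baseline to month 3 or month 6.* Baseline precedes PTH, and every subject is on PTH at both later visits. There is no arm without PTH, so this is an uncontrolled before-after comparison. It is also the aim written for these tests.
- *Pump versus injection.* Months 3 and 6 each close one randomised period, so this is the only randomised contrast that the tests can give. No analysis of it is written out for these measures.

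Hiding the regimen from testers can protect the second comparison. It cannot protect the first, because a tester would know that the subject is on PTH at both later visits.

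**Step 2. What do the stated expectations point to?**

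The regimen hypothesis favours the pump, but on tolerability, convenience and preference. The pump's predicted physiological advantages in Objectives concern minerals, bone and kidney. The improvement hypothesised in Summary of Protocol is for PTH as such; it applies equally at months 3 and 6 and cancels in the pump-injection difference. No text predicts better strength or walking on the pump. A general leaning towards the pump is documented; a leaning on these two tests is not.

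**Step 3. How large could the effect be?**

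The documents give no SD, effect size or power for these tests. The only power figure, in the sample size justification, concerns serum calcium and has no bearing here. The calculation below is therefore an illustration.

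Inputs:
- n = 24 pairs, the total enrolment, or n = 8, the adults enrolled first. For Biodex, 24 is a ceiling, because subjects with right knee or elbow pathology are excluded from it.
- Two-sided 5% paired t test. This is an assumption; the 0.05 level is stated only for serum calcium.
- No true pump-injection difference.
- Expectation shifts the mean paired difference by d times the SD of that difference, with d = 0.1, 0.25 or 0.5. This too is an assumption.

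Formula: the false-positive rate is P(|T| > c), where T has a noncentral t distribution with n − 1 degrees of freedom and noncentrality d√n, and c is the 97.5% point of the central t distribution.

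| n | c | d | d√n | False-positive rate |
|---|---|---|---|---|
| 24 | 2.069 | 0.1 | 0.490 | 7.6% |
| 24 | 2.069 | 0.25 | 1.225 | 21.7% |
| 24 | 2.069 | 0.5 | 2.449 | 65.0% |
| 8 | 2.365 | 0.1 | 0.283 | 5.7% |
| 8 | 2.365 | 0.25 | 0.707 | 9.4% |
| 8 | 2.365 | 0.5 | 1.414 | 23.2% |

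Using n − 2 degrees of freedom, to allow for a period term, moves each figure by less than one percentage point.

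**The case against.** The strongest reply is that the point protects a contrast the protocol does not set for these tests. Their written aim is relief from PTH, the study calls itself a pilot, and the measures are secondary. This stands as a limit on the point's weight. It does not remove the point: comparing pump with injection is the purpose of the trial, and data from the end of each period invite that comparison.

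Second, subjects know their regimen and supply the effort, so masked testers leave part of the bias in place. That stands in full.

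Third, the walk-run test follows a published method, which may already standardise encouragement. What that method covers cannot be seen here, and it is not cited for Biodex.

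Fourth, the size rests wholly on an assumed shift, and on every tester knowing the regimen and leaning the same way. That also stands. At 0.1 SD the inflation is slight.

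A reader might infer more than the documents support in two ways:
- *That the testers do know the regimen.* The text never says so; it is silent. Appendix 2, to which the Medications section refers for pump therapy, is not in the supplied text, so silence is confirmed only for what was supplied.
- *That the protocol predicts better function on the pump.* As step 2 shows, the improvement it predicts is for PTH, and its hopes for the pump concern other outcomes.

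**Conclusion.** The point holds as a cheap improvement and not as a flaw that threatens the trial. Two effort-dependent secondary tests are run without any stated masking of testers, in a department that could plausibly be kept unaware of the regimen. That leaves the pump-injection comparison on these tests open to tester expectation. The stated before-after PTH aim is unaffected, and its own weakness, the lack of a control without PTH, is a separate matter.

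The size cannot be estimated from the documents. The range of about 8% to 65% with 24 pairs, or 6% to 23% with 8, shows how sensitive the comparison would be to an assumed shift of 0.1 to 0.5 SD. It is not an estimate of the bias in this trial. That masking is feasible is also an inference, since the supplied text does not say where the pump is worn.

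**What to change.** In Enrollment and Baseline Data Collection (Rehabilitation Medicine paragraph) and in Monitoring of Subjects, state that:

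1. the Rehabilitation Medicine staff who run and score the walk-run and Biodex tests are not told the regimen or the sequence;
2. pump or injection sites are kept covered where the test allows, bearing in mind that Biodex eligibility requires intact skin at the right knee and elbow;
3. subjects are asked not to mention their regimen to the tester;
4. the month-3 tests are done before the switch at the second admission;
5. the tester records at each visit whether the regimen became known.

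For the analysis, estimate pump minus injection within subject, allowing for period, and use all tests. A plain comparison of month 3 with month 6 will not do: in a two-sequence crossover that is the period contrast. Report how often masking failed. Treat any analysis that leaves out unmasked tests as descriptive only. Leaving them out breaks pairs and selects on an event after randomisation that may be commoner with a worn device.

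The cost is a short instruction to an existing department and one item on the test form, with no added staff or visits. Masking will sometimes fail. Subjects' own expectation still acts on effort and on the fatigue questionnaire, so only the tester's part of the bias is removed.
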